9.4 Secondary outcome analyses

9.4.1 Time to complete wound closure

The analysis will use the Cox proportional hazards model to determine time to event (healing). Subjects who withdraw from treatment will be entered into the analysis and censored at the time they withdraw from the trial or are lost to follow up. The analysis will consider covariates that might influence the outcome in the trial. Factors considered potentially important in predicting the outcome of treatment will be tested in a Cox model. Stepwise elimination of non significant covariates will be undertaken and only those covariates that remain statistically significant will be retained in the model. Tests of proportionality will be undertaken using graphical (Nelson Aalen) and quantitative methods (Schoenfeld test). The data will be presented graphically using Kaplan Meier graphs. The

results of the multivariable analysis will be presented as Hazard ratios together with 95% confidence intervals and p-values generated from the model.

9.4.2 *Change in wound size*

An important secondary outcome measure is partial wound healing, which is a function of wound area and perimeter change. Care must be taken to choose an appropriate measure for this outcome, as measures such as reduction in area or percentage reduction in area usually lead to biased comparisons. It is proposed that the trial uses the linear healing measure of Gowland-Hopkins & Jamieson⁴⁴ and described in Gilman⁴⁵. This measure is defined as:

$$d = \Delta A/p_{avg}$$

where ΔA is the change in wound area between two successive visits and p_{avg} is the average of the wound perimeters measured at these two visits. 'd' will be calculated weekly after randomization to treatment.

Comparisons of the two treatment groups will be carried out in terms of d, at each of these assessments. An unpaired t test will be carried out at each assessment, to test the hypothesis that the treatment groups do not differ in terms of d, against the alternative hypothesis that the treatment groups differ in terms of d. A 95% confidence interval for the difference between treatment groups in terms of 'd' will be calculated, based on the t test results.

9.4.3 *Wound recurrence rate.*

The wound recurrence rates will be analyzed with a time to event strategy as in 9.4.1.

9.4.4 *Incidence of amputation*

Fisher's Exact Test will be used. An approximate 95% confidence interval for the difference between treatment groups in terms of amputation rate will be estimated using the normal approximation interval.

9.4.5 *Safety and Tolerability*

Safety and tolerability data will be presented in summary form and in detailed data listings. No significance testing will be applied to these data.

9.5 *Missing and Spurious Data*

No procedures are planned for the imputation of missing data. Subjects with missing data will be omitted from the relevant analyses.

If main outcomes are missing every attempt should be made to discover why and rectify wherever possible. If it is still not possible to discover the outcomes then the reason for this must be recorded e.g. death, refusal, incapacity.

For the health economic analysis it is standard procedure to impute missing data where necessary in order that an appropriate estimate can be given of the total costs of care.

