6.3. Standard Care Treatment

Subjects in both groups will receive the same standard care regime that includes sharps debridement of all callus/necrotic tissue, AMWT and off-loading, where it is required. In a multi-center trial the value of study site consistency in standard care regimens within a trial cannot be over-emphasized because of the profound effects these procedures have on clinical outcome for chronic wounds.²³ Consistency in standard care regimens is important for minimizing variability and allowing assessment of treatment effect. Every attempt will be made to minimize deviations from the procedures described in the protocol and subject compliance recorded in CRFs.

In order to minimize variability in standard of care between sites:

- All centers will perform a standardized training before the trial
- All centers will be monitored closely by a study site monitor and the study director

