9 STATISTICAL ANALYSIS

9.1 Sample Size and Power Analysis

All sample size estimations in this section of the protocol were undertaken using the sampsi function in Stata 11 (Statcorp LP, Texas, USA). Comparisons of groups was made assuming no continuity correction.

Little data are available on similar studies using topical oxygen therapy within randomized clinical trials making sample size estimation problematic. Large trials of dermal substitutes and negative pressure have been undertaken that can be used to indicate the potential healing in the control group. The three large trials have control healing of between 18% and 28.9% around 12 weeks after entering the trial, with a mean of 28%.^{25,27,29}

The expected improvement in healing using the active device is more problematic as there have been few comparative studies published. Aburto and Frye undertook a randomized study of 20 venous ulcers and 20 diabetic foot ulcer patients.⁴² Topical oxygen demonstrated higher healing in the DFU patients after 90 days of 90% versus 40% in the control group. Blackman et al randomized 28 patients with DFUs and obtained a similar response (82.4% versus 45.5%).²² The potential difference between treatment groups was therefore 50% and 36.9% respectively. Using these studies a total sample size of 28 and 52 would be expected based on 80% power at the 5% level of significance. Neither of these studies was blinded. It is therefore likely that the effect is likely to be substantially smaller than that experienced in these two studies.

Because of the small size of these trials and lack of blinding it has been decided to offer a more cautious approach to the calculation of sample size based on a smaller expected benefit of oxygen therapy. By combining the results of the two randomized studies already undertaken the control group achieved a healing rate of 9/21 (42.8%). In the actively treated group healing occurred in 23/27 (85.2%). Assuming an expected control rate of 43% and a difference of half that experienced in these trials of 21% (to 64%) would require a sample size of 88 patients in each group (total=176), with a power of 80% and a level of significance set at $p<0.05$.

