In order to overcome the uncertainty surrounding the expected benefit, the trial will be undertaken using group sequential design (GSD) allowing for interim analysis to be performed at intervals during the trial recruitment. The interim analysis will take place after one third of subjects have been recruited, after two thirds and then a final analysis at full recruitment. The Pocock method of interim analysis will be used, which requires an equal level of significance ($p<0.022$) over the three analyses.⁴³ If the difference in primary outcome produces a probability less than this in any of the analyses then the null hypothesis is rejected and the alternative hypothesis of a difference in healing has been shown. In order to achieve this level of significance a total of 110 patients need to be recruited to each arm of the trial (total=220).

Since all patients will achieve a 12 week end point (healed versus unhealed) no uprating of this sample size will be made to take into consideration patients lost to follow up (see section 9.2).

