9.3 Primary outcome analysis

The primary endpoint is the “Incidence of complete wound closure within 12 weeks”.

The null hypothesis to be tested is that there is no difference between treatment groups in terms of the rate of wound healing after 12 weeks of study treatment. The alternative hypothesis is that such a difference exists.

Uncorrected Chi squared analyses will be used to determine the difference between treatment groups in terms of wound closure rate within 12 weeks, at the interim analysis. 95% confidence intervals will be estimated using the normal approximation interval.

Logistic regression analysis will be used to determine the effects of confounding on the primary outcome at the trial end. In particular, gender, age, ulcer duration, size and diabetic factors will be considered in the model. A stepwise procedure will be used to eliminate non-significant covariates from the model. The effect of different centers' outcomes will be entered as a random effect into the model.

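### Section 9.4.1 does not say how center enters the Cox model for time to closure; a shared frailty kept out of stepwise elimination would match 9.3 and protect a few points of power if centers differ

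*Combined protocol and SAP*

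**What the plan says.** Time to complete closure is the first secondary endpoint listed in section 3.3.2. For its analysis, section 9.4.1 says: "The analysis will use the Cox proportional hazards model to determine time to event (healing"). Covariates come from an unnamed list of factors thought likely to matter. Stepwise elimination follows, and only statistically significant covariates stay. The section mentions no center term, frailty or stratification, and it does not rule center out. Section 9.4.3 applies the same strategy to recurrence.

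Section 9.3 treats binary closure within 12 weeks differently. After the stepwise rule for the logistic model, a separate sentence says that the centers' "outcomes will be entered as a random effect into the model".

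Section 6.3 asks for consistent standard care across sites "because of the profound effects these procedures have on clinical outcome for chronic wounds". The synopsis allows up to 30 centers. Section 5 describes central permuted blocks and does not mention stratification by center.

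**The concern.** Both analyses use index-ulcer closures in the same subjects at the same centers. The plan gives center a place in one model and is silent in the other. If the analyst adds center through the open list, the significance rule can remove it; with about 7 subjects per center (220/30 = 7.3), it could easily be dropped. Whether and how center enters would then be settled after the data are seen.

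If closure hazards differ between centers, a Cox model without center estimates a population-average hazard ratio, which lies closer to 1 than the within-center ratio, and center differences stay in the noise. At stake are some power on a secondary endpoint and a clear statement of what the hazard ratio means beside the center-adjusted odds ratio from 9.3.

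**Working it through.** **Inputs from the documents.** Section 9.1: "Assuming an expected control rate of 43% and a difference of half that experienced in these trials of 21% (to 64"%), then "with a power of 80% and a level of significance set at $p<0.05"; "Comparisons of groups was made assuming no continuity correction"; and, for the group sequential design, "an equal level of significance ($p<0.022$) over the three analyses", giving 110 per arm. The test is two-sided, since 9.3 says "The alternative hypothesis is that such a difference exists". No between-center variance, hazard ratio, event count or power for time to closure is given.

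**Reproducing the plan's sample size.** Pooled-variance formula, with mean rate (0.43 + 0.64)/2 = 0.535:

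n per arm = [z(α/2)·√(2 × 0.535 × 0.465) + 0.8416·√(0.43 × 0.57 + 0.64 × 0.36)]² / 0.21²

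- α = 0.05: (1.960 × 0.7054 + 0.8416 × 0.6896)² / 0.0441 = 87.4, so 88 per arm, 176 in total.
- α = 0.022: (2.290 × 0.7054 + 0.8416 × 0.6896)² / 0.0441 = 109.3, so 110 per arm, 220 in total.

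Both match section 9.1.

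**Power for time to closure without center effects.** Under constant proportional hazards:

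- Hazard ratio = ln(1 − 0.64)/ln(1 − 0.43) = 1.82.
- Expected closures = 110 × (0.43 + 0.64) = 117.7.
- Schoenfeld power at two-sided 5% = Φ(√(117.7/4) × ln 1.8175 − 1.960) = Φ(1.28) = 90.0%. At 0.022 it is 82.9%.

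**Effect of center, by simulation.** There were 220 subjects assigned at random to 30 centers, 1:1 in blocks of 4 not stratified by center, with exponential closure times censored at 12 weeks. Center effects were normal on the log hazard. Overall closure was held at 43% and 64% for every SD, with 1,500 trials per setting and two-sided 5%. The frailty variance was treated as known, which is the best case for the frailty model.

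| Assumed center SD | Within-center HR | HR without center | Power without center | Power, shared frailty | Power, stratified by center |
|---|---|---|---|---|---|
| 0 | 1.82 | 1.84 | 90.1% | 90.1% | 83.1% |
| 0.2 | 1.83 | 1.82 | 89.0% | 88.9% | 82.7% |
| 0.3 | 1.86 | 1.82 | 89.7% | 89.6% | 84.1% |
| 0.5 | 1.93 | 1.84 | 91.0% | 93.0% | 89.1% |
| 0.7 | 2.03 | 1.85 | 90.1% | 94.1% | 91.6% |
| 1.0 | 2.25 | 1.85 | 90.8% | 97.0% | 95.3% |

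Monte Carlo error on power is about 0.8 points.

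**Frailty variance estimated rather than known** (600 trials per setting, same overall rates). Power without v with frailty was 88% v 88% at SD 0 and 91% v 92% at SD 0.3. The gains were about 2 points at 0.5, 4 at 0.7 and 4.5 at 1.0. Having to estimate the variance therefore cost nothing visible when centers do not differ.

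**Type I error** (53.5% closure in both arms, 3,000 trials per setting, Monte Carlo error √(0.05 × 0.95/3,000) = 0.4 points). Without center: 5.1%, 5.7% and 5.3% at SD 0.3, 0.5 and 1.0. With a known-variance frailty: 4.8%, 5.5% and 6.0%. Neither model shows a clear problem, although the 6.0% is a reason not to lean on the largest gain in the table.

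**The case against.** Four counter-arguments have weight.

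- **Silence is not exclusion.** A reader might infer that 9.4.1 leaves center out. It does not say so: the list is open, and large center differences are where a tested center term is most likely to survive. What stands against this is that nothing protects center from elimination and nothing fixes its form.
- **The result without center is not an error.** A reader might infer a biased hazard ratio or an invalid test. The table shows a population-average ratio of 1.82 to 1.85, close to the 1.82 implied by the design, with about nominal type I error. Choosing a marginal or a conditional effect is legitimate. Section 9.3 itself uses an unadjusted chi-squared test at the interim and a center-adjusted model at the end.
- **A large power loss is not supported.** If 43% and 64% are read as rates in an average center, a separate simulation gives power without v with center of 89% v 89% at SD 0.3, 84% v 87% at 0.5 and 80% v 87% at 0.7. The fall to 80% arises because overall rates then shift as the SD grows. Section 9.1 takes its 43% from pooled study totals, so these are overall rates; holding them fixed keeps power without center at 89% to 91%.
- **The larger SDs imply very uneven centers.** Around a 43% control rate, 1 − 0.57^exp(±1.96 × SD) puts the middle 95% of centers at about 27% to 64% for SD 0.3, 19% to 78% for 0.5 and 13% to 89% for 0.7. Sections 6.3 to 6.3.3 also plan training, monitoring, central photograph review and a restricted dressing list to limit such differences. The true SD may be small, and the gain then nil.

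The cost objection does not stand for a shared frailty. It does stand for stratification, which loses about 7 points at SD 0 and about 2 at SD 0.5.

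**Conclusion.** The point holds as a minor improvement to a secondary analysis. Section 9.4.1 should fix the role of center in advance, as 9.3 does. From a base near 90%, the gain from a shared frailty is essentially nil at a center SD of 0.3 or below, about 2 points at 0.5, about 4 at 0.7 and about 4 to 6 at 1.0, with no loss at SD 0. The documents do not support saying that the planned hazard ratio is wrong, that the error rate is inflated, or that power falls well below the design value.

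These figures rest on an assumed between-center SD, constant proportional hazards, all 30 centers open with random sizes, continuous rather than weekly closure times, and no other covariates. The primary endpoint and the sample size of 220 are unaffected.

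**What to change.** Add to section 9.4.1 that:

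- center enters the Cox model as a shared frailty, with its distribution named;
- the frailty is exempt from stepwise elimination;
- the reported hazard ratio is a within-center effect, in line with 9.3;
- center is not used as a stratification factor, because up to 30 centers averaging about 7 subjects would lose power.

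Extend the frailty to 9.4.3 only if the number of recurrences supports it. Only healed subjects are at risk there, about 118 at the design rates, and the documents give no expected recurrence count.

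The cost is one extra variance parameter and a conditional reading of the hazard ratio. No new data, visits or subjects are needed.

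### The Cox model for time to closure takes its covariates by stepwise significance from an open list, does not say that randomized arm stays in, and has no unadjusted result beside it

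*Combined protocol and SAP*

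**What the plan says.** Section 9.4.1 analyses time to complete wound closure, the first secondary endpoint listed in 3.3.2, with a Cox model. On candidate covariates it says only: "Factors considered potentially important in predicting the outcome of treatment will be tested in a Cox model". The selection rule is: "Stepwise elimination of non significant covariates will be undertaken and only those covariates that remain statistically significant will be retained in the model". On reporting, the "results of the multivariable analysis will be presented as Hazard ratios together with 95% confidence intervals and p-values generated from the model". The only display that does not depend on selection is descriptive: "The data will be presented graphically using Kaplan Meier graphs".

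Section 9.4.1 gives no covariate list, stepwise direction or removal threshold. It does not say that randomized arm is kept whatever its p-value, and it names no log-rank test or unadjusted Cox model. No other section fixes the Cox covariates.

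Two other sections are affected. For recurrence, 9.4.3 says: "The wound recurrence rates will be analyzed with a time to event strategy as in 9.4.1". For the primary endpoint, 9.3 does name candidates for the logistic model ("gender, age, ulcer duration, size and diabetic factors will be considered in the model"), but leaves the diabetic factors undefined and also selects: "A stepwise procedure will be used to eliminate non-significant covariates from the model".

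**The concern.** A Cox hazard ratio depends on what else is in the model. Adjusting for a prognostic factor generally moves it further from 1 even when the arms are perfectly balanced, so each covariate set targets a slightly different quantity. If the outcome data choose the set, the plan does not fix which treatment effect will be reported. The interval and p-value come from the last model as though it had been chosen in advance.

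The silence about arm matters more. Read literally, the elimination rule could remove treatment when it is not significant, leaving no treatment hazard ratio or interval to report. No unadjusted analysis is planned to fall back on.

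**Working it through.** **Inputs from the documents.** 12-week closure 43% (control) and 64% (active), 110 per arm, 80% power, no continuity correction (9.1). Interim looks after 73 and 146 subjects (9.6).

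**Check on the planning figures.** Section 9.4.1 states no figure of its own, so the sample size is reproduced first. Per arm, n = [z(α/2)·√(2p̄q̄) + z(β)·√(p₁q₁ + p₂q₂)]² / δ², with p̄ = 0.535 and δ = 0.21:
- α = 0.05: (1.960 × 0.7054 + 0.842 × 0.6896)² / 0.0441 = 87.4, so 88, as stated.
- α = 0.022: (2.290 × 0.7054 + 0.842 × 0.6896)² / 0.0441 = 109.3, so 110, as stated.

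**Implied hazard ratio and closures.** Under proportional hazards, HR = ln(1 − 0.64) / ln(1 − 0.43) = ln 0.36 / ln 0.57 = 1.82. Expected closures are 110 × (0.43 + 0.64) = 117.7 at full enrolment, 73 × 0.535 ≈ 39 at the first look and 146 × 0.535 ≈ 78 at the second.

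**Chance that a real covariate survives.** For a continuous factor with hazard ratio h per SD and D closures, tested at two-sided 0.05, the chance of retention is about Φ(√D · ln h − 1.96). At D = 117.7, √D = 10.85.

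| h per SD | 1.1 | 1.2 | 1.3 | 1.4 | 1.5 |
|---|---|---|---|---|---|
| Retained | 18% | 51% | 81% | 96% | 99% |

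For example, h = 1.2 gives Φ(10.85 × 0.1823 − 1.96) = Φ(0.02) = 51%. At the first look, h = 1.3 gives Φ(6.25 × 0.2624 − 1.96) = Φ(−0.32) = 37%.

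**Simulation of the written rule.** Assumptions that the documents do not supply: backward elimination at p < 0.05, exponential hazards, censoring at 12 weeks, five independent normal candidates (one null, four real) and no centre effect. N = 220, control closure 43%, true HR 1.82, arm forced in except in the last row.

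| | Weak (1.1–1.2) | Moderate (1.2–1.3) | Strong (1.5) |
|---|---|---|---|
| At least one real factor dropped | 99% | 84% | 5% |
| Distinct sets seen, of 2⁵ = 32 | 30 | 31 | 10 |
| Share of the commonest set | 17% | 16% | 88% |
| Mean HR: unadjusted / full / stepwise | 1.79 / 1.84 / 1.83 | 1.75 / 1.84 / 1.82 | 1.65 / 1.86 / 1.85 |
| Power: full / stepwise | 88.2 / 88.8% | 88.0 / 87.7% | 89.3 / 89.6% |
| Stepwise v full HR: median / 95th percentile difference | 1.9 / 6.8% | 1.6 / 6.5% | 0.6 / 3.4% |
| Significance differs, stepwise v full | 2.6% | 2.6% | 0.7% |
| Arm eliminated if not forced in | 11% | 12% | 10% |

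Replicates: 1000, 2000 and 1000. With moderate effects, coverage was 94.6% (full) and 94.1% (stepwise). Under the null, type I error was 4.7% (full) and 5.7% (stepwise, Monte Carlo SE about 0.4 points) with moderate effects, and 5.6% and 5.3% with strong effects. An arm that is not forced in was eliminated in about 95% of null trials.

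**Second simulation.** Seven candidates (HR per SD 0.70, 0.80, 0.90, 1.0, 0.90, 0.85, 1.0) with weekly closure times gave power of 84.9% unadjusted, 89.2% stepwise and 90.0% fixed, mean HR 1.80 stepwise against 1.82 fixed, and type I error of 5.0%. The factor with HR 0.80 was dropped in 35 to 42% of trials.

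**The case against.** The strongest reply is that, with arm kept in, almost nothing happens to the treatment comparison. That stands. Randomization protects the test, and stepwise selection recovers most of what adjustment offers: 89.2 − 84.9 = 4.3 of 90.0 − 84.9 = 5.1 points in the second simulation. In two of the three settings tabulated, its rejection rate was slightly above the full model's. A reader might infer that the p-value is badly inflated or that substantial power is lost; neither calculation supports that.

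A reader might also infer that the plan will routinely discard factors known to predict closure. The documents give no covariate effects and do not say that ulcer size or duration predicts closure; 9.3 only names them for consideration. How often real factors are dropped depends on assumed effects, and the problem nearly disappears if all of them are strong.

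It is also fair that this is a secondary endpoint. The stopping rule and rejection of the null hypothesis rest on the primary outcome (9.1), tested at the interim analysis by an uncorrected chi-squared test (9.3). Most statisticians would assume that treatment stays in the model. That is the natural reading, but the text does not say so.

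Finally, the model recommended below is not the one simulated: it has five covariates and a centre effect across up to 30 sites. The power figures above should not be quoted for it.

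**Conclusion.** The point holds as a failure of prespecification with an inexpensive remedy. The only treatment hazard ratio planned for time to closure comes from a data-selected model, its interval ignores the selection, and nothing guarantees that arm remains in it. Recurrence inherits the rule.

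If arm is forced in, the size is modest: a median HR shift of about 2% (95th percentile about 7%) with weak or moderate effects, power loss of 0.3 to 0.8 points where there is a loss, and type I error of 5.0 to 5.7%. If it is not, arm is eliminated in about 12% of trials at HR 1.82 with moderate effects. That is simply the complement of power (100 − 88), so the effect estimate would go missing exactly when the result is not significant.

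The instability of the selected set rests on assumed effects of HR 1.1 to 1.3 per SD, a 0.05 threshold and full enrolment. Stopping early would make selection less reliable. None of this touches the sample size or the interim test of the primary endpoint.

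**What to change.** In 9.4.1 and 9.4.3:
- Delete stepwise elimination and state that randomized arm is always retained.
- Fit one Cox model with covariates fixed before unblinding, using the factors that 9.3 already names: baseline ulcer size, ulcer duration, age, gender and one defined diabetic factor such as HbA1c. Handle centre as in 9.3, as a random effect.
- Report the unadjusted Cox hazard ratio or a log-rank result alongside.
- Name a shorter list, for example ulcer size and duration, for use if the trial stops at the first look, and for recurrence, where events may be few (the documents give no rate).

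The shorter list is needed because arm plus five covariates is six terms. That gives 118 / 6 ≈ 20 closures per term at full enrolment and 78 / 6 = 13 at the second look, but only 39 / 6 = 6.5 at the first. Arm plus two covariates restores 39 / 3 = 13.

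Make the same change to the stepwise logistic model in 9.3 and define the diabetic factors there.

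The cost is wording. Baseline ulcer area (7.1.1), wound history, demographics and HbA1c (8.1.1, 8.2.1) are already collected. No data, visits or subjects are added.

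### Section 9.4 tests four efficacy secondaries, one of them at every weekly visit, with no order, gate on the primary, significance level or exploratory label

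*Combined protocol and SAP*

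**What the plan says.** All references are to the combined protocol and SAP.

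- **Primary (9.1).** "The Pocock method of interim analysis will be used, which requires an equal level of significance", namely p<0.022 at each of three analyses. This level is tied to the primary outcome only.
- **Time to closure (9.4.1).** Cox model with stepwise covariate elimination; the "results of the multivariable analysis will be presented as Hazard ratios together with 95% confidence intervals and p-values generated from the model".
- **Change in wound size (9.4.2).** The linear healing measure d is calculated weekly. An unpaired t test is done at each assessment "to test the hypothesis that the treatment groups do not differ in terms of d, against the alternative hypothesis", with a 95% interval. The section calls partial healing an important secondary outcome.
- **Recurrence (9.4.3).** "The wound recurrence rates will be analyzed with a time to event strategy as in 9.4.1".
- **Amputation (9.4.4).** "Fisher's Exact Test will be used", with an approximate 95% interval for the difference.
- **Where testing is switched off.** Section 9.2 rules out inferential tests of baseline values. For safety (9.4.5), "No significance testing will be applied to these data".

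No section gives the four efficacy secondaries a significance level, an order, a condition on the primary, an alpha split or an exploratory label. Section 9.4 gives no separate timing either, so they would be read at whichever look ends the trial.

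**The concern.** The plan disclaims testing for baseline and safety data and controls repeated testing for the primary. The efficacy secondaries receive neither treatment, so they stand as formal tests. If the primary misses 0.022, nothing stops a report from presenting a secondary with p<0.05 as a positive efficacy result, with no stated error rate behind it.

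Two features make this more than a formality. Wound size alone brings up to 12 tests, and the plan does not say which week counts. Time to closure is built from the same closure events as the primary, but no passage holds it to the level that the primary must meet.

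**Working it through.** **1. The plan's own figures.** Inputs from 9.1: closure 43% v 64%, no continuity correction, "with a power of 80% and a level of significance set at" 0.05. With p̄ = 0.535,

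n per arm = [z(1−α/2)·√(2p̄(1−p̄)) + z(0.80)·√(p₁q₁ + p₂q₂)]² / (p₂ − p₁)²

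- α = 0.05: [1.960 × 0.7054 + 0.8416 × 0.6896]² / 0.0441 = 87.4, so 88 per arm (176), as stated.
- α = 0.022: [2.290 × 0.7054 + 0.8416 × 0.6896]² / 0.0441 = 109.3, so 110 per arm (220), as stated.
- Simulating three looks at 0.022 gives an overall two-sided error of 5.0%. The primary is controlled.

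**2. Counting the secondary tests.** Time to closure 1, wound size up to 12 (weekly over a 12-week treatment phase), recurrence 1, amputation 1: about 15. With one wound-size test there would be 4.

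**3. Chance of at least one p<0.05 under the global null.** Assumption: two-sided 5% per test. If independent, the chance is 1 − 0.95^k:

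- k = 4: 1 − 0.8145 = 18.5%
- k = 12 (wound size alone): 46%
- k = 15: 53.7%

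The documents give no correlations, so these are assumed. Simulation with one common correlation ρ:

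| ρ | 4 tests | 15 tests |
|---|---|---|
| 0 | 18.5% | 54% |
| 0.3 | 17.5% | 46% |
| 0.5 | 15.6% | 36% |
| 0.7 | 13.0% | 26% |
| 0.9 | 9.4% | 14% |

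If instead only the weekly d tests are strongly related to each other, and at most weakly (0 or 0.3) to time to closure, the 15-test figure is 45–48% at ρ = 0.3 and 22–26% at ρ = 0.9.

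**4. Fisher's test.** It is conservative when events are rare. At 110 per arm its true size is 0.06%, 0.6%, 2.3% and 3.0% for assumed amputation rates of 1%, 2%, 5% and 10%. For three independent 5% tests plus Fisher at size f, the chance is 1 − 0.95³(1 − f): 14.3% at f = 0 and 16.8% at f = 3%. So the four-test figure falls somewhat but stays well above 5%.

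**5. Time to closure at the stopping look.** Trials were simulated with looks at 73, 146 and 220, exponential closure times seen weekly to week 12, and a log-rank test standing in for the Cox test (stepwise selection not modelled).

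- Under the null, p<0.05 occurs in about 7% of trials (7.1–7.4% over closure rates of 20–54%). Read at 0.022, the figure is 4.2–4.6%.
- The correlation with the primary statistic is 0.975–0.998. Splitting the 7% on that basis, about 4.8–5.0 points fall in trials where the primary has already falsely rejected. About 2.2–2.4 points fall where it has not.

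**The case against.** The strongest reply is that the plan makes no confirmatory claim from the secondaries. Its only reject/accept rule, its sample size and its efficacy stopping rule all concern the primary. Section 9.4 states no level, and a 95% interval does not imply a 5% decision rule here: 9.3 also attaches 95% intervals to the primary, which is judged at 0.022. This stands in part. The 5% reading is an assumption, and the inflation matters only if secondary p-values are used as claims. The plan does not rule that use out, however, and it does rule out testing for baseline and safety data.

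Three stronger readings are tempting and are not supported:

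- **A single inflation figure, such as about 16%.** For four tests this needs a correlation near 0.5, or a particular size for Fisher's test. The documents supply neither. It also counts wound size once, although 9.4.2 orders weekly tests.
- **Time to closure as a large second chance at the primary question.** Most of its 7% coincides with a false rejection of the primary. The extra false-positive chance is about 2.2–2.4 points.
- **A false-positive rate under the planned effect.** With 43% v 64%, about 6.5% of simulated trials show time to closure p<0.05 without primary rejection. The effect is real in that scenario, so those are not false positives.

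**Conclusion.** The omission is real: four efficacy secondaries are formally tested with no multiplicity rule and no label limiting their use. If they are read at two-sided 5%, the chance of at least one false positive under the global null is about 9–19% with one test per endpoint, and lower if amputations are rare. With the weekly wound-size tests as written it is roughly 14–54%. These ranges rest on assumed correlations and an assumed 5% level. The independent-test values of 18.5% and 54% are the upper ends of their ranges. The primary result is not threatened. The weakness lies in what may be claimed from the secondaries, chiefly after a failed primary, so this should be corrected but does not undermine the trial.

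**What to change.** Add one paragraph to 9.4 before any unblinded look, for example:

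> Secondary efficacy hypotheses are tested only if the primary null hypothesis is rejected. They are tested in this order: time to complete closure; the difference in d at one named assessment (or one named summary of d); recurrence; amputation. Each is tested at p<0.022 at the look at which the primary was rejected, stopping at the first non-significant result. The remaining weekly comparisons of d and all other secondary outcomes are reported as estimates and intervals without claims of significance.

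The order shown is an example. What matters is that it is complete and that a single wound-size comparison is named, since otherwise the largest source of multiplicity remains.

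The alternative is to state that all analyses in 9.4.1–9.4.4 are exploratory and support no confirmatory claim.

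Either change needs no patients or data. Under the gated version, a secondary with p between 0.022 and 0.05, or any secondary after a failed primary, could no longer be claimed as significant. Under the exploratory label, no secondary could be.
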